12.6.2 Optional and allowed concomitant medication

Allopurinol or other approved uric acid-lowering agent is allowed to use in patients with high risk of tumor lysis syndrome due to high tumor burden. Adequate hydration must be given to reduce the risk of tumor lysis and renal impairment with these patients. Mycostatin and oral fluconazole may be used at the investigator's decision. Antiemetics and antidiarrheal drugs are recommended to use as necessary. Granulocyte growth factors are allowed to use in neutropenia in accordance with ASCO Guidelines, but they are not to be given prophylactically. Red cell and/or platelet transfusions and erythropoietin are allowed to use according to institutional guidelines if clinically needed and patients can have bisphosphonates by recommended guidelines.

12.6.3 Prohibited and/or restricted treatments

Other anti-myeloma treatment than study protocol treatment during the study is not allowed. Glucocorticoids are allowed for nonmalignant situation like asthma with a dose of no more than ≤ 4 mg/day dexamethasone or prednisone ≤ 20 mg/day.

12.7 Study drug assignment

This is an open-label study without any randomization or stratification. All patients will use the same study treatment protocol.

12.8 Study drug packaging, labeling and ordering

Carfilzomib

Study drug carfilzomib will be delivered free of charge from Amgen covered with final study label on packages based on subscriptions of each study site. Study sites

will document a drug medication diary during protocol treatment, including dose, batch number, shelf life and amount.

Lenalidomide

Lenalidomide 25mg will be taken orally with the morning breakfast. Study sites will document a drug medication diary during protocol treatment, including dose, batchnr, shelf life and amount. This drug will be reimbursed as routine medication, with labelling written locally by the treating physician in the study:

Dexamethasone

Dexamethasone 40 or 20 mg will be taken orally with the morning breakfast. Study sites will document a drug medication diary during protocol treatment, including dose, batch number, shelf life and amount. This drug will be reimbursed as routine medication, with labelling written locally by the treating physician in the study.

12.9 Study compliance

Study drug will be administered or dispensed only to eligible patients under the supervision of the investigator or identified sub-investigator(s). The appropriate study personnel will maintain records of study drug receipt and dispensing. The personnel will maintain accountability records of study drug, including information such as study drug name, dose/strength, batch number, date and no. of capsules dispensed, date and no. of capsules returned and finally date destroyed.

12. STUDY ASSESSMENTS AND PROCEDURES

Study investigations will be done by the sample flowchart Table 1.

13.1 Medical previous history

- complete medical history
- present symptoms
- history of thrombosis of the patient
- history of any other malignancies of the patient
- performance status (ECOG)
- recent infections

- bone symptoms
- bleeding
- polyneuropathy
- gastrointestinal symptoms

13.2 Physical examinations

- standard physical examination with cardiovascular and targeted neurological (polyneuropathy, autonomic neuropathy) examinations
- blood pressure
- body weight and height, surface area
- investigation for infections and bleedings

13.3 Hematology

hemoglobin, hematocrit, leukocytes, leukocyte differential count, neutrophils, platelets

13.4 Blood chemistry

Blood, bone marrow and urine samples will be sampled according to the flow chart.

13.5 Immunochemistry

Serum protein electrophoresis and immunofixation (IFE) at study entry, start of every cycle and every two months until progression. 24-h urine electrophoresis and immunofixation at study entry, the start of every cycle and every two months until progression. Serum free light chains (S-FLC) at study entry, start of every cycle and at every two months until progression

13.6 Bone marrow assessment

Bone marrow sample will be collected at entry for multiparameter flow cytometry (MFC), and one month after Cycle 4 day 28. It is important to collect the first pull and no more than 2 mL to avoid haemodilution, where after the aspiration is put into an EDTA tube. Bone marrow aspirate and biopsy will be collected and analyzed one month after Cycle 4 day 29 and every time CR/sCR are suspected.

13.7 Specific additional investigations

- Bone imaging: PET-CT at screening. Patients with avid lesions will receive the protocol treatment. A subsequent PET-CT will be performed at Visit D1.
- Electrocardiogram from all patients at entry, and if clinically indicated
- MRD analysis by Euroflow at entry and at visit after C4D29.
- Patient reported QOL forms (The European Organisation for Research and Treatment of Cancer Quality of life questionnaire (EORTC QLQ-C30) + question of shortness of breath filled in at screening, before each cycle of KRd, at day 15 of each KRd cycle, at one and three months after end of KRd, and at end of treatment (Progressive disease). The EORTC QLQ-CIPN20 questionnaire evaluating peripheral neuropathy will be filled in at C1D1 and Visit D1.
- Pregnancy tests will be performed monthly from study start until 4 weeks after end of treatment with carfilzomib/lenalidomide.

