| SJS | stevens-johnson syndrome |
| SPMs | second primary malignancies |
| SUSAR | suspected unexpected severe adverse event |
| TEN | toxic epidermal necrolysis |

| | |
|------|---|
| TTNT | time to next treatment |
| VCD | bortezomib cyclophosphamide dexamethasone |
| VGPR | very good partial response |
| VRD | bortezomib lenalidomide dexamethasone |
| VTD | bortezomib thalidomide dexamethasone |
| VTE | deep vein thrombosis |

STUDY PROCEDURES

| | Screening (Day -28-0) | Day 1 Cycle 1 | Day 15 Cycle 1-4 | Day 1 Cycle 2-4 | Day 2, 8, 9, 15,16 Cycle 1-4 | Visit D1 C4D29 +/- 2 days | Visit D2 one month after D1 +/- 2 days | Every second months +/- 7 days | EOT at PD | Every 3m after PD until death |
|--|--------------------------|------------------|---------------------|--------------------|------------------------------------|---------------------------------|--|--|--------------|--|
| Medical/treatment history | X | | | | | | | | | |
| Complete physical examination, including height | X | | | | | | | | | |
| Targeted physical examination | | X | | X | X | X | X | X | X | |
| Vital Signs ^a | X | X | | X | X | X | | | | |
| Hematology ^b | X | X | X | X | | X | X | X | X | |
| Comprehensive blood chemistry panel ^c | X | X | | X | | X | X | X | X | |
| Evaluation of clonal disease ^d | X | X | | X | | X | X | X | X | |
| Safety assessment, AEs | X | X | | X | X | X | X | X | X | |
| Targeted neurologic evaluation | X | X | | X | X | X | X | X | X | |
| Quality of life evaluation | | X | X | X | | X | X | | X | |
| BM aspiration for MRD Euroflow | | X | | | | X | | | | |
| PET-CT | X | | | | | | X | | | |
| ECG | X | | | | | | | | | |
| ECHO cor, if clinically indicated | X | | | | | | | | | |
| Pregnancy test in fertile women | X | X | | X | | X | X | X | X | |
| Use of diuretics | X | X | | X | X | X | | | | |
| Overall survival | | X | | X | X | X | X | X | X | X |

^a Heart rate, blood pressure, temperature, weight

^b Neutrophils, hemoglobin, platelets

^c Hematology, SR, CRP, Potassium, Sodium, Total calcium, ionized calcium, magnesium, phosphate, creatinine, estimated GFR, ASAT, ALAT, gGT, ALP, LD Trop T, Pro-BNP, Bilirubin, Glucose, Albumin, Total protein, Uric acid

^d Serum and urine electrophoresis with immune fixation; serum free light chains; bone marrow aspirate/biopsy if CR/sCR is suspected from last visit

Introduction

| | |
|---|-----------|
| 1.1 Scientific background | 10 |
| 1.2 MRD measurement | 10 |
| 1. STUDY DRUGS..... | 11 |

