7. INVESTIGATIONAL PLAN – STUDY DESIGN

This is an investigator initiated, academic, non-randomized, open-label multicenter study for consolidation in patients with multiple myeloma after standard first line treatment.

CONPET vs 14, 24th October 2018

After a standard induction regime with ASCT, patients can be included in the study. A PET-CT will be performed, patients with a negative PET result will go out of the study, with a strong recommendation of standard-of-care treatment, as specified below. Patients with a positive PET result will receive four cycles of KRd followed by standard-of-care treatment with lenalidomide maintenance 10-15mg once daily

A new PET-CT-evaluation will be performed after completed consolidation. At inclusion in the study, MRD samples will be taken from all patients. We will repeat these samples after completed consolidation. The goals of the study are to evaluate what proportion of patients are PET-positive after standard first line treatment and how many of these can become PET-negative after KRd consolidation. The study will explore the dynamics of MRD status in this setting, and the correspondence between these two methods. Review of PET-CTs will be central and blinded.

The PET-CT-negative group will have long time follow up through their local doctor for PFS and OS

The study is a phase 2 study, with 50 PET-positive patients, to show the feasibility, safety and efficacy of this design.

Inclusion of patients will continue until 50 PET-positive patients have been included.

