12.4 Lenalidomide treatment after the four KRd cycles

Lenalidomide will be given according to the approved maintenance label for post-transplant patients, i.e. 10-15 mg daily continuously.

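### Section 13.7 requires monthly pregnancy tests until four weeks after lenalidomide ends; the flow chart goes two-monthly after Visit D2 and stops at end of treatment

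*Protocol*

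**What the plan says.** Four places in the protocol bear on the testing schedule.

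- **Section 13.7 (Specific additional investigations):** "Pregnancy tests will be performed monthly from study start until 4 weeks after end of treatment with carfilzomib/lenalidomide".
- **Study procedures flow chart, row "Pregnancy test in fertile women":** the test is marked at screening, Day 1 of cycle 1, Day 1 of cycles 2 to 4, Visit D1 (C4D29), Visit D2 (one month after D1), the visits every second month (window 7 days either way), and end of treatment at progression. The column for three-monthly contact after progression is blank.
- **Chapter 12 (Study assessments and procedures):** "Study investigations will be done by the sample flowchart Table 1".
- **Section 12.4, on the maintenance phase:** "Lenalidomide will be given according to the approved maintenance label for post-transplant patients, i.e. 10-15 mg daily continuously". Chapter 7 (Investigational plan) says the same of PET-positive patients: "Patients with a positive PET result will receive four cycles of KRd followed by standard-of-care treatment with lenalidomide maintenance 10-15mg once daily".

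**The concern.** Section 13.7 ties the end of monthly testing to the end of treatment with carfilzomib/lenalidomide. Lenalidomide continues daily after cycle 4, so on its plain wording the monthly requirement continues through maintenance and for four weeks beyond. The flow chart has no monthly visit after D2 and no test after the end-of-treatment visit.

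A site that works from the flow chart, as chapter 12 directs, would do about half of the tests that section 13.7 requires during maintenance and would miss the final one. A monitor working from section 13.7 could record each missing test as a deviation, although the site had followed the protocol's own schedule.

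The protocol treats pregnancy exposure as serious elsewhere. It requires a negative serum test before inclusion (8.1), highly effective contraception until 30 days after the last study drug (12.6.1), and permanent discontinuation with 24-hour reporting if pregnancy is found (14.6). The testing schedule that supports these rules should be unambiguous.

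**Working it through.** The plan gives no figure to reproduce. The check reads the flow-chart row against its column headings and counts tests.

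**Step 1. The two sources side by side**

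| Period | Section 13.7 | Flow chart |
|---|---|---|
| Screening to cycle 4 (28-day cycles) | monthly | screening and Day 1 of each cycle |
| Visit D1 (C4D29) | monthly | marked |
| Visit D2 (one month after D1) | monthly | marked |
| After D2, on lenalidomide | monthly | every second month, 7 days either way |
| End of treatment at progression | within the testing period | marked |
| Four weeks after end of treatment | end of the testing period | no visit and no mark |

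The sources agree up to D2 and diverge after it. The row has a cell for every column, so the blank cells are not a reading artefact.

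**Step 2. Number of tests after D2**

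Let m be the months on lenalidomide after D2.

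- Section 13.7: m / 1 tests.
- Flow chart: m / 2 tests.
- Ratio: (m / 2) / m = 0.5, whatever the value of m.

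The protocol gives no maintenance duration. Taking m = 12 for illustration gives 12 / 1 = 12 tests against 12 / 2 = 6.

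**Step 3. Length of the gaps**

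- Monthly: 365 / 12 ≈ 30 days.
- Every second month: 365 / 6 ≈ 61 days.
- Each of two neighbouring visits may shift by 7 days, so the gap ranges from 61 − 14 = 47 to 61 + 14 = 75 days.

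**Step 4. The final test**

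Section 13.7 carries testing to four weeks after treatment ends. The flow chart's last mark is at end of treatment. The next column is contact every three months after progression, which chapter 10 describes as telephone follow-up for survival. No scheduled visit could therefore host the four-week test.

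**Step 5. Does the end of treatment in section 13.7 include maintenance?**

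Four features of the text say that it does:

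- The quality-of-life item in section 13.7 refers to the end of KRd when it means the four cycles, and separately to an end of treatment that it equates with progressive disease. The pregnancy item uses the second kind of wording and names lenalidomide, the drug that continues.
- The flow chart places end of treatment at progression.
- The heading of section 12.4 calls maintenance lenalidomide treatment, and the section sits in the treatment chapter.
- Section 12.6.3 bars anti-myeloma treatment other than protocol treatment during the study, so maintenance lenalidomide is most naturally protocol treatment.

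**The case against.** The strongest objection is that section 13.7 may mean only the end of the KRd combination. The synopsis lists four cycles and no maintenance, chapter 7 calls maintenance standard of care, and section 12.4 refers to the approved label. The synopsis also speaks of completed treatment where it seems to mean KRd. The timing fits: tests on Day 1 of each cycle, at D1 and at D2 are monthly, and D2 falls about four weeks after cycle 4 ends. The two-monthly tests would then be additional, and there would be no shortfall.

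This reading is possible, but the wording set out in step 5 counts against it. It also leaves a mismatch, because section 13.7 would end testing at about D2 while the flow chart continues to progression. On either reading the two sources define different testing periods.

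A second objection is that a table of visits does not forbid tests between them, so a site could satisfy both by following section 13.7. That is true, and the pointer in chapter 12 does not say that the flow chart overrides explicit text. But the pointer sends sites to the flow chart without qualification, and the flow chart provides no occasion for the extra tests.

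Two mitigating points stand. Section 12.6.1 requires highly effective contraception and, if a menstrual period is missed, interruption of study drug and a serum test. The number of women of childbearing potential among the 50 treated patients is not stated and is probably small. These points limit the consequence but do not remove the contradiction.

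**Conclusion.** The concern holds. After Visit D2 the flow chart gives half the pregnancy tests that section 13.7 requires (about 6 against 12 over an illustrative 12 months), with gaps of about 61 days (47 to 75) against about 30. It also omits the test four weeks after treatment ends.

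The halving rests on reading the end of carfilzomib/lenalidomide treatment as including maintenance, which the wording favours but does not settle beyond doubt. On the narrower reading the sources still disagree on how long testing continues.

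The point concerns safety conduct. It affects no endpoint, sample size or analysis, and probably few patients. It should be corrected because it concerns pregnancy prevention and the correction is small.

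**What to change.** Reconcile the flow chart, section 13.7 and the pointer in chapter 12 so that they give:

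- one testing frequency during lenalidomide maintenance;
- one time for the final test, with a visit or other arrangement in the flow chart at which it can be done;
- an explicit statement of whether the end of treatment in section 13.7 includes maintenance.

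The frequency and the final time are for the sponsor to decide; this review does not favour either schedule. The cost is a correction to one flow-chart row with a footnote, or to one sentence of section 13.7. If the reconciled schedule keeps tests between the two-monthly visits, sites will also need a way to do and record them.

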13. SAFETY

Study investigators must follow the study protocol treatment and follow the dose reduction and adjustment guidelines in every study patient. Dose interruptions and modifications from other reasons can be performed at physician's discretion. Exceptional issues should be discussed with the principal investigator. Adverse event will be documented if observed, mentioned during open questioning, or when spontaneously reported.

14.1 Adverse Event Reporting

All Serious Adverse Events (SAEs) that occur following the subject's written consent to participate in the study through 60 days of discontinuation of dosing must be reported to AMGEN. AEs occurring in the same period will be registered.

Intensity for each SAE, including any lab abnormalities, will be determined by using the NCI CTCAE version 4.0 (v4.03. June 14, 2010), as a guideline, whenever possible. The criteria are available online at <http://ctep.cancer.gov/reporting/ctc.html>.

14.2 Adverse Events

- An Adverse Event [AE] is defined as any new untoward medical occurrence or worsening of a pre-existing medical condition in a patient or clinical

investigation subject administered an investigational (medicinal) product and that does not necessarily have a causal relationship with this treatment. An AE can therefore be any unfavorable and unintended sign (including an abnormal laboratory finding, for example), symptom, or disease temporally associated with the use of investigational product, whether or not considered related to the investigational product.

- The causal relationship to study drug is determined by a physician and should be used to assess all adverse events (AEs). The causal relationship can be one of the following:
 - Related: There is a reasonable causal relationship between study drug administration and the AE.
 - Not Related: There is not a reasonable causal relationship between study drug administration and the AE.
- The term “reasonable causal relationship” means there is evidence to suggest a causal relationship.
- Adverse events can be spontaneously reported or elicited during open-ended questioning, examination, or evaluation of a subject. (In order to prevent reporting bias, subjects should not be questioned regarding the specific occurrence of one or more adverse events).

14.3 Serious Adverse Events

A **Serious Adverse Event (SAE)** is any untoward medical occurrence at any dose that:

- results in death
- is life-threatening (defined as an event in which the subject was at risk of death at the time of the event; it does not refer to an event which hypothetically might have caused death if it were more severe)
- requires inpatient hospitalization or causes prolongation of existing hospitalization
- results in persistent or significant disability/incapacity
- is a congenital anomaly/birth defect

- is an important medical event, defined as a medical event that may not be immediately life-threatening or result in death or hospitalization but, based on appropriate medical and scientific judgment, may jeopardize the subject or may require intervention (e.g., medical, surgical) to prevent one of the other serious outcomes listed above. Examples of such events include but are not limited to intensive treatment in an emergency department or at home for allergic bronchospasm; blood dyscrasias or convulsions that do not result in hospitalization.

Suspected transmission of an infectious agent (e.g., pathogenic or non-pathogenic) via the study drug is an SAE.

Although pregnancy, overdose, cancer and potential drug induced liver injury (DILI) are not always serious by regulatory definition, these events must be handled as SAEs.

The following hospitalizations are not considered SAEs:

- Elective surgery planned before signing consent
- Admissions as per protocol for a planned medical/surgical procedure
- Routine health assessment requiring admission for baseline/trending of health status (e.g., routine colonoscopy)
- Medical/surgical admission other than remedying ill health state that was planned before study entry. Appropriate documentation is required in these cases
- Admission encountered for another life circumstance that carries no bearing on health status and requires no medical/surgical intervention (e.g., lack of housing, economic inadequacy, caregiver respite, family circumstances, administrative reason)

14.3.1 Serious Adverse Event Collecting and Reporting

If any SAE occurs during the study it need to be reported on the SAE form in the web-CRF. For each SAE, the investigator will provide the following information: type of event, date initiated/observed, severity, action taken, outcome and possible relation to study medication. The forms will be provided to and be kept by the

sponsor. SAE forms will be available to the independent monitor. All SAEs should be reported to the sponsor-investigator within 24 hours after the investigator has been aware of the SAE. The investigator should take all appropriate measures to ensure the safety of the patients. He or she should follow up the outcome of SAE until resolution of the patient's condition

All SAEs must be collected that occur during the screening period and within 60 days of discontinuing dosing. If applicable, SAEs must be collected that relate to any later protocol-specific procedure (such as follow-up skin biopsy).

The investigator should report any SAE occurring after these periods that is believed to be related to study drug or protocol-specified procedure. An SAE report should be completed for any event where doubt exists regarding its status of seriousness.

If the investigator believes that an SAE is not related to study drug but is potentially related to the conditions of the study (such as withdrawal of previous therapy, or a complication of a study procedure), the relationship should be specified in the narrative section of the SAE Report Form.

SAEs, whether related or unrelated to the study drug, and pregnancies, must be reported to AMGEN within 24 hours. SAEs must be recorded on the SAE Report Form; pregnancies on a Pregnancy Surveillance Form. The study secretariat in Oslo will report to Amgen. If an SAE is clearly related to the progression of myeloma, the SAE should not be reported.

If only limited information is initially available, follow-up reports are required. (Note: Follow-up SAE reports should include the same investigator term(s) initially reported.)

If an ongoing SAE changes in its intensity or relationship to study drug or if additional information becomes available, a follow-up SAE report should be sent within 24 hours to the sponsor-investigator using the same procedure used for transmitting the initial SAE report.

All SAEs should be followed to resolution or stabilization.

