Allergic Reactions: Cases of allergic reaction/hypersensitivity reactions have been reported.

Severe skin reactions: Stevens-Johnson syndrome (SJS) and toxic epidermal necrolysis (TEN) have been reported. Lenalidomide must be discontinued for angioedema, grade 4 rash, exfoliative or bullous rash, or if SJS or TEN is suspected, and should not be resumed following discontinuation for these reactions. Discontinuation of lenalidomide should be considered if skin rash \geq grade 2 is exfoliative or bullous or if SJS or TEN is suspected. for other forms of skin Lenalidomide should not be resumed following discontinuation for these reactions.

Musculoskeletal and connective tissue disorders: The rare AE of rhabdomyolysis has been observed with lenalidomide. The reports of rhabdomyolysis were confounded by concurrent use of statins and dexamethasone, concurrent viral and bacterial infections, trauma, and serotonin syndrome, which are risk factors for rhabdomyolysis.

Neoplasms benign, malignant and unspecified. Second primary malignancies:

NDMM: In clinical trials of NDMM an increase of invasive SPMs, most notably AML and MDS, has been observed predominantly in subjects receiving lenalidomide in combination with melphalan or immediately following high-dose melphalan and ASCT. The incidence rate was 1.57 per 100 person-years for the combined MPR arms and 0.36 per 100 person-years for the MP+p control arm. Cases of B-cell malignancies were observed in clinical trials where subjects received lenalidomide in

the post-ASCT setting. Patients should be carefully evaluated before and during treatment using standard cancer screening for occurrence of SPMs, and treatment should be instituted as appropriate.

Post-marketing data: Pneumonitis, transient abnormal liver laboratory tests, hyperthyroidism, hypothyroidism, TLS, TFR and allergic conditions including angioedema, SJS and TEN have been identified and are considered by Celgene to be at least possibly related to lenalidomide.

Lactose intolerance: Revlimid capsules contain lactose. Patients with rare hereditary problems of galactose intolerance, the Lapp lactase deficiency or glucose-galactose malabsorption should not take this medicinal product.

Unused capsules: Patients should be advised never to give this medicinal product to another person and to return any unused capsules to their pharmacist at the end of the treatment.

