10. END OF STUDY

Inclusion in the study ends when 50 patients have had positive initial PET-CT results. After progressive disease, patients will be followed by telephone for overall survival. Patients with negative PET-CT results will be followed by telephone/fax for progressive-free survival and overall survival every second month (± 7 days).

The study will end with last patients last visit. There will be a post-study follow-up for overall survival in all patients, both with initial PET-CT positivity and negativity.

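### After a 60-day limit counted from an undefined end of dosing, second primary malignancies are collected by attribution rather than occurrence, and the collection rules conflict

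*Protocol*

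**What the plan says.** **The risk.** Section 2.3 reports that invasive SPMs, notably AML and MDS, rose "predominantly in subjects receiving lenalidomide in combination with melphalan or immediately following high-dose melphalan and ASCT". It expresses the risk in person-time: "The incidence rate was 1.57 per 100 person-years for the combined MPR arms and 0.36 per 100 person-years for the MP+p control arm". It also instructs that "Patients should be carefully evaluated before and during treatment using standard cancer screening for occurrence of SPMs". Section 8.1 requires prior ASCT, and treated patients receive lenalidomide within KRd and then as maintenance (sections 7 and 12.4).

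**Status of a new cancer.** Section 14.3: "Although pregnancy, overdose, cancer and potential drug induced liver injury (DILI) are not always serious by regulatory definition, these events must be handled as SAEs".

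**Rules that close early.** Section 14.3.1: "All SAEs must be collected that occur during the screening period and within 60 days of discontinuing dosing". Sections 14.1 and 14.4.2 give the same 60 days. Section 14.5 stops non-serious events at 30 days. After the window, section 14.3.1 says "The investigator should report any SAE occurring after these periods that is believed to be related to study drug or protocol-specified procedure".

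**Rules that run longer.** Section 14.3.1 also says "If any SAE occurs during the study it need to be reported on the SAE form in the web-CRF", and the synopsis runs the study until every patient has progressed. The study procedures table marks adverse-event assessment at Visit D1, Visit D2, every second month and at end of treatment on progression.

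**After progression.** Section 10: "After progressive disease, patients will be followed by telephone for overall survival". In the procedures table, the three-monthly contacts after progression carry the survival row only.

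**The concern.** SPMs accrue with follow-up time, while the period in which every SAE is recorded whatever its cause may be short. Beyond it, whether a new cancer enters the database depends on a causality judgement. Section 14.2 asks for evidence suggesting a causal link to study drug, and in this population two other explanations are always available: the earlier transplant conditioning, and maintenance lenalidomide, which section 7 describes as standard of care.

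Safety is a listed endpoint and part of the stated purpose of the trial (section 16.1). If sites apply the shorter rule, late SPMs are counted by attribution and the count is biased downwards. If some sites apply the shorter rule and others the longer one, the count also mixes two definitions, and it is unclear which person-time belongs in the denominator.

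**Working it through.** The protocol gives no expected SPM count, so there is no planned figure to reproduce. Two quantities can be worked out: how much SPM risk lies outside the cause-independent window, and how much lies outside any scheduled adverse-event contact.

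**Inputs from the protocol.** 50 treated patients (section 7); four 28-day cycles (section 12.1); 60 days (section 14.3.1); SPM rates of 1.57 and 0.36 per 100 person-years (section 2.3).

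**Assumptions.** Constant SPM hazard; deaths and losses ignored; follow-up F of 3-5 years (wider range 2-8); median PFS of 2-5 years, exponential. The protocol gives neither F nor a median PFS. The 1.57 rate comes from the combined MPR arms, not a post-ASCT group, and 0.36 is that comparison's control arm, so counts are illustrative. The shares do not depend on the rate.

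**Step 1: window if dosing means the four KRd cycles.**
- 4 × 28 + 60 = 172 days; 172 / 365.25 = 0.471 years.
- 50 × 0.471 = 23.5 person-years.
- Expected SPMs inside: 23.5 × 0.0157 = 0.37 (at 0.0036: 0.08).

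**Step 2: share arising after the window closes, 1 − 0.471/F.**

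| F (years) | Person-years | Expected SPMs at 1.57 (at 0.36) | Share after closure |
|---|---|---|---|
| 2 | 100 | 1.57 (0.36) | 76% |
| 3 | 150 | 2.35 (0.54) | 84% |
| 5 | 250 | 3.92 (0.90) | 91% |
| 8 | 400 | 6.28 (1.44) | 94% |

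Using 172 days slightly favours the protocol. The last scheduled dose is cycle 4 day 22, which is study day 3 × 28 + 22 = 106, so the window would close at day 166.

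**Step 3: share covered by visits with a scheduled adverse-event assessment.** Mean time to progression within F is (1 − e^(−λF))/λ, with λ = ln 2 / median PFS.

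| F (years) | Median PFS 2 years: before / after progression | Median PFS 5 years: before / after progression |
|---|---|---|
| 3 | 62% / 38% | 82% / 18% |
| 5 | 48% / 52% | 72% / 28% |
| 8 | 34% / 66% | 60% / 40% |

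For example, at median 2 and F = 5: λ = 0.347, mean = 2.38 years, and 2.38/5 = 48%.

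**Step 4: alternative reading of dosing.** If maintenance counts and lenalidomide runs to progression, the window closes 60 days after that. The share outside it is then a little below the after-progression figures in Step 3, not 84-91%.

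**Step 5: the rules set against each other.** On the KRd-only reading, the window closes at about day 166. Visit D1 is day 113, and the first two-monthly visit falls at about day 174 counted from Visit D1, or about day 204 counted from Visit D2, visit tolerances aside. The two-monthly adverse-event assessments therefore fall in a period for which sections 14.1 and 14.3.1 require no cause-independent record, although the opening rule of 14.3.1 does.

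**The case against.** A reader might infer that every later contact records survival only and that most SPMs would be missed. The document does not support either inference. In treated patients the two-monthly visits and the end-of-treatment visit carry an adverse-event assessment, with examination and blood tests; only contacts after progression are limited to survival. The opening rule of section 14.3.1, read with the study duration in the synopsis and the cancer rule in 14.3, makes an SPM before progression reportable whatever its cause. Attributed SAEs stay reportable with no end date, and section 2.3 alerts investigators to the risk.

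The meaning of dosing is also open. The procedures table and section 13.7 equate end of treatment with progression, and maintenance has its own subsection under treatment (12.4). Both favour a window that runs through maintenance. Section 7 points the other way by calling maintenance standard of care.

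These points stand, and they limit the finding. They do not remove it. The longer rule sits in the same section as the shorter one, and nothing says which prevails. The duty to report attributed events still counts by attribution. The one-year SUSAR period in 14.4.2 applies only to events not listed in the reference documents, so it is an uncertain backstop for a risk the protocol already describes. It would be speculation to say that investigators will blame earlier melphalan and stay silent; the protocol merely leaves room for it. Nor is a denominator wholly lacking, since assessed time to progression could serve.

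PET-negative patients receive no study drug and leave the study under section 7, so SPM collection in them would be an extension rather than a correction.

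**Conclusion.** The point holds as a conflict in the collection rules with a likely downward effect on the SPM count in treated patients. Cause-independent collection ends 60 days after an undefined event, a later SPM need be recorded only if attributed, and no contact after progression provides for recording one.

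If dosing means the four KRd cycles, about 84-91% of a constant SPM hazard over an assumed 3-5 years (76-94% over 2-8 years) arises after that window closes. This is the share exposed to attribution-based reporting, not the share lost. If adverse-event visits to progression are fully credited, about 18-52% of person-time over 3-5 years (28-66% over 5-8 years) has no adverse-event contact, under median PFS of 2-5 years. The bias itself cannot be sized, because the protocol gives no basis for how often late SPMs would be judged related.

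Expected numbers are small: about 2.4-3.9 in total over 3-5 years at the higher rate and 0.5-0.9 at the lower. The data can only be descriptive and cannot separate four KRd cycles from maintenance. The amendment is worth making, but the gap does not threaten the primary endpoint.

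**What to change.** 1. In section 14.3.1, exempt SPMs from the 60-day limit. Record type and date of diagnosis of any new malignancy in treated patients, regardless of causality, from first dose to death or last contact.
2. Use contacts already scheduled: the two-monthly visits, the end-of-treatment visit and the three-monthly contacts after progression.
3. Capture it in one eCRF field completed by the investigator. Section 14.2 bars questioning patients about specific adverse events, so a direct question would need an explicit exemption there.
4. Define dosing for safety collection, stating whether maintenance lenalidomide counts, and reconcile the procedures table with sections 14.1, 14.3.1, 14.4.2 and 14.5.
5. Report SPMs descriptively, as a number and per 100 person-years over the follow-up in which they were sought.

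The cost is one eCRF field and modest extra SAE paperwork, with no new visits or tests. Collecting the same item at the two-monthly telephone or fax contacts of PET-negative patients is optional.
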